A cross-sectional, observational feasibility study which will provide a descriptive evaluation of the quality of life (QoL) of atrial fibrillation (AF) patients experiencing a bleed, both in primary care and hospital settings (wards and emergency department (ED)). No control patients (i.e. no-bleed patients) will be enrolled as part of this feasibility phase.

Objective(s):

Primary objective

- To test the feasibility of identifying patients with both minor and major bleeds as a result of anticoagulant treatment for AF and evaluating their QoL through both primary and secondary care settings.

Secondary Objectives

- To describe and interpret the observed differences in QoL by type of bleed.
- To describe the treatment received and the nature of the bleed experienced by the patient.
- To undertake structured qualitative interviews to gain detailed insight into issues from a patient perspective, for those who live with AF and have experienced a recent bleed while taking anticoagulants.
- To observe appropriateness of three chosen PROMs (EQ5D, AFEQT and PACT-Q, part 2) in capturing QoL data, specifically post a bleeding event for AF patients who are taking anticoagulants.

Outcome measure(s):

Primary outcome measures

- The study will be considered feasible if recruitment efforts prove successful:
 - A sample size of 50-80 patients will be required for the study in line with the guidance outlined in the Lancaster et al (2004) publication regarding feasibility studies¹. A minimum of 50 patients recruited will deem the study as successful.

- Patient reported outcome measures (PROMs) will be used in the study using a survey design to collect QoL data from patients directly in both primary and secondary care settings. Three validated questionnaires will be used in this study: EQ5D, AFEQT and PACT-Q. All questionnaires have previously been used in atrial fibrillation studies to collect QoL data.

Secondary outcome measures

- Patients will be asked to provide their anticoagulant medication information along with full details of the bleed they have experienced, which will be used to later categorise the bleeds as minor or major by a medical professional, during the data cleaning and analysis. Medication and bleed details will be recorded before each patient completes the selected study PROMs.

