All patients will be asked to complete three questionnaires for the study: EQ-5D-5L, Perception of Anticoagulant Treatment Questionnaire, **Part 2 only** (PACT-Q, Part 2) and Atrial Fibrillation Effect on QualiTy-of-life (AFEQT), which should take no longer than 30 minutes in total to complete^{23, 39}. Considerations have been made, as far as possible, to minimize impact on patient's time. Questionnaires will be conducted at two time-points for this study; an initial round will be completed at point of consent/enrolment and a second identical set of questionnaires at 90±14 days post-enrolment. Patients will complete the initial round of questionnaires immediately after consent process, to ensure that loss to follow-up is controlled. An option to take part in a further qualitative interview, after the 90-day follow up, will be included in both questionnaire sets. Initial questionnaires will be provided electronically via tablet devices or on paper copies, if patients prefer. Follow-up questionnaires will be sent out either through the post 3 weeks prior to the 90-day follow-up date, along with a stamped addressed envelope for ease of return or enrolled patients who prefer to complete data collection electronically will be sent a survey link. Patients will be asked in an accompanying letter to complete and return the questionnaires within the 90±14 day time-frame. If no reply is received within 2 weeks of first correspondence, a reminder letter along with a second copy of all questionnaires will be delivered. The PROMs for the study have been carefully selected based upon study requirements and desired outcomes as far as possible, in lieu of having access to a validated bleed-specific QoL questionnaire. Data collected using the chosen questionnaires will also allow comparable analysis with more substantial databases, as data will line up with previously collected QoL data in AF patients, where identical questionnaires have been widely used.

Patient Interviews

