To capture valuable, emotive data in the form of patient thoughts and feelings in relation to the study objectives, a small subset of patients will complete short, structured interviews, which will be conducted by research staff at Swansea Trials Unit. It is anticipated that 10 interviews will be sufficient to identify key themes from patients. Interviews will stop if saturation is reached before then and no new themes are identified; interviewees will be randomly selected from all patients who have indicated that they would be willing to take part. Any patient who has consented to be interviewed *and* completed initial questionnaires as a minimum, will be contacted (i.e. patients who fail to complete a second set of questionnaires at 90±14 days can still take part in study interviews, if contacted successfully). However, patient interviews will only take place after the 90-day follow-up point post-enrolment. Interview

questions will be designed in close collaboration with the study's consultant haematologist to ensure that appropriate questions are asked in a concise and respectful way. Patients will be asked to expand more specifically on bleeding events and consequent level of impact on quality of life **at time of event (bleed)** in comparison to the effect **3 months (90 days) later**. Additionally, patients will be asked to give opinions on the chosen study PROMs on relevance to the true burden of AF and if the questionnaires have overlooked any important quality of life concerns for patients with AF. Recall bias will be managed as far as conceivable by ensuring that interviewers are sufficiently experienced in conducting interviews efficiently and interview questions are impartial. Any information given by patients during an interview will be verified where possible.

All interviews will be recorded upon patient consent and transcribed at a later date. Interview questions will be identical across all patients.

Data Handling & Storage

Paper copies of CRFs and questionnaires will be transcribed into the study database, where the data will be checked for consistency and accuracy, alongside other data collected electronically.

Data will be hosted securely on the REDCap data management system (licensed to Swansea Trials Unit (STU)). Study data will be held anonymously within REDCap and any identifying data (including protected characteristics) will be kept separately, secured by access restrictions.

Data Analysis and Reporting

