4.1 Progression Criteria

The feasibility of the trial methods, recruitment strategies, and its potential to be further developed and into a full qualitative study will be measured on key progression criteria. These criteria have been approved by our Trial Steering Committee and study managers, where applicable:

- Minimum requirements met for recruitment (50 eligible patients)
- Retention of at least 50% of enrolled patients at follow-up
- 70% PROMs data completion at baseline and 40% completion of PROMs at follow-up

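### The synopsis declares the study a success on 50 recruits alone, while section 4.1 judges feasibility on recruitment, retention and PROM completion

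*Protocol*

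**What the plan says.** The synopsis, under primary outcome measures, makes feasibility depend on recruitment going well and then fixes the bar: "A minimum of 50 patients recruited will deem the study as successful". It lists collection of PROM data as a primary outcome measure too, but attaches no threshold to it and none to retention.

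Section 4.1 of the protocol measures feasibility on three bullets holding four thresholds. The first is recruitment of 50 eligible patients. The second is "Retention of at least 50% of enrolled patients at follow-up". The third is "70% PROMs data completion at baseline and 40% completion of PROMs at follow-up". Retention has enrolled patients as its base. The completion bars have no stated base, and neither retention nor completion is defined there.

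Section 2.1 gives the primary objective two parts: finding and recruiting the patients, and measuring their QoL. Section 3.1 schedules "a second identical set of questionnaires at 90±14 days post-enrolment", returned by the patient on paper or through a survey link. It also provides that "patients who fail to complete a second set of questionnaires at 90±14 days can still take part in study interviews, if contacted successfully".

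**The concern.** A feasibility study exists to support a decision, so its success rule should give one answer for one set of data. Here the synopsis and section 4.1 apply different tests to the same question. A team that recruits well and follows up badly could report the study as successful by citing the synopsis, while section 4.1 says the follow-up criteria were missed. That gap matters because section 1.2 hypothesises a sustained effect of bleeding on QoL, and a larger study of that question depends on usable day-90 data. If the choice between the two rules is left until results are known, it can follow the results.

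The missing base for the 40% bar adds a smaller uncertainty of the same kind: two readers could apply it to the same counts and disagree.

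**Working it through.** **Inputs.** Recruitment bar 50, retention bar 50% of enrolled, completion bars 70% and 40% (protocol section 4.1); success at 50 recruited (synopsis). The bars are set, not derived, so there is no calculation in the plan to reproduce.

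**Step 1: the two rules applied to the same outcome, 50 enrolled.** For this table only, a return counts as both retained and complete, and enrolled patients are the base.

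| Day-90 returns | Synopsis | Retention (bar 50%) | Follow-up PROMs (bar 40%) |
|---|---|---|---|
| 0 | success | 0/50 = 0%, not met | 0/50 = 0%, not met |
| 10 | success | 10/50 = 20%, not met | 10/50 = 20%, not met |
| 24 | success | 24/50 = 48%, not met | 24/50 = 48%, met |
| 25 | success | 25/50 = 50%, met | 25/50 = 50%, met |

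The synopsis column never changes, because its rule does not use follow-up data. In the first two rows both follow-up criteria fail. In the third row they split, and section 4.1 does not expressly say that every criterion must be met.

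**Step 2: the base of the 40% bar, 50 enrolled.**

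- Of enrolled patients: 0.40 × 50 = 20.
- Of the minimum number with baseline PROMs: 0.70 × 50 = 35, then 0.40 × 35 = 14, which is 14/50 = 28% of enrolled.
- Of the minimum number retained: 0.50 × 50 = 25, then 0.40 × 25 = 10, which is 10/50 = 20% of enrolled.

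The exact (Clopper-Pearson) 95% interval is 26% to 55% for 20/50 and 10% to 34% for 10/50. As an example of disagreement, 26 retained with 12 complete gives 12/26 = 46% (met) or 12/50 = 24% (not met).

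**Step 3: does the 40% bar add anything to the 50% retention bar?** Take enrolled patients as the base.

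- If retained means a fully completed set, the two counts are equal, and 25 or more retained always exceeds 20. The 40% bar then adds nothing.
- If retained means any return, completion can fall below retention. With 25 retained and 19 complete, retention is 50% (met) and completion is 19/50 = 38% (not met). To meet both bars at the minimum retention, 20/25 = 80% of those retained must have complete PROMs. The 40% bar then does separate work.

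**The case against.** Four arguments deserve an answer.

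**The two texts serve different purposes.** The synopsis speaks of the study being successful, and section 4.1 of its potential for further development. It would be wrong to infer that the synopsis authorises proceeding to a larger study on recruitment alone; it says nothing about proceeding. This narrows the conflict but does not remove it, because both texts say what makes the study feasible and set different tests.

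**The definitions may be in a statistical analysis plan.** That is fair for the denominator, for what counts as a complete PROM and for the meaning of retention, so their absence from the protocol does not carry this point. Such a plan would not remove the conflict between the synopsis and section 4.1, since both statements stand in the protocol.

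**The natural base is already clear.** The bullet above the completion bars names enrolled patients, and at baseline that is the obvious base. The reading of 10 of 50 needs an unstated switch of base and retention at its exact minimum. It is possible but strained.

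**The bars are coherent as they stand.** A reader might infer that the 40% bar is either redundant or satisfied by 10 of 50. The protocol does not force that choice, as 25 retained with 19 complete shows. Nor does it equate retention with a completed set: it asks that "Patients will be asked in an accompanying letter to complete and return the questionnaires within the 90±14 day time-frame", but a set can come back partly filled, and a patient who misses it may still be interviewed. Overlap is likely, since the questionnaire set is the only day-90 collection scheduled for all patients. Identity is an inference.

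It is also natural to read the section 4.1 list as applying jointly, though one added clause would settle it.

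**Conclusion.** The conflict between the synopsis and section 4.1 is real and rests on no assumption beyond the wording of both. Once 50 patients are recruited, the synopsis rule is met at any level of follow-up, from none to all. Section 4.1 asks for at least 25 of 50 retained and, with enrolled patients as the base, 35 of 50 with baseline PROMs and 20 of 50 with follow-up PROMs. The synopsis therefore leaves the QoL part of the primary objective without a test.

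The base of the 40% bar is a supporting clarification. Its range at 50 enrolled is 10 to 20 patients, with 20 the most natural reading; the lower figures assume a different base, at its minimum. Whether the bar adds to the retention criterion depends on what retained means, so the documents do not support calling it redundant. The study is descriptive and the remedy is brief, so this is a modest but worthwhile correction to the decision rule.

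**What to change.** 1. In the synopsis, limit the sentence about 50 recruits to the recruitment criterion, and state that feasibility is judged on all section 4.1 criteria together.
2. In section 4.1, repeat that all criteria must be met, and name enrolled patients as the base for both completion bars. At 50 enrolled this means 35 at baseline and 20 at follow-up.
3. Define retained as any day-90 return, so that the 40% bar tests something beyond the retention bar.
4. Report completion for each of the three instruments separately. A single all-three-complete figure would hide differences between them, and judging the suitability of each PROM is a secondary objective.

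The cost is a few lines of wording, agreed by the Trial Steering Committee before follow-up data are seen. No extra data or patients are needed. The downside is that success becomes somewhat harder to declare than under the synopsis rule.

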5 STUDY LIMITATIONS/STRENGTHS

The study will enhance limited, existing knowledge of the level of impact that bleeding while anticoagulated have on patients who have been diagnosed with AF taking anticoagulants.

As this is a feasibility study, it is difficult to predict how successfully eligible patients will be identified and subsequently enrolled, based on the study inclusion/exclusion criteria. There is also uncertainty around optimal ways to promptly identify patients within the primary care and hospital settings. Patients who experience minor bleeds do not always routinely discuss these events with GPs and identifying these patients could prove challenging. Recruitment measures will be tested during this pilot study to inform best strategies for a possible larger-scale study in the future.

As yet, there is no known validated PROM which specifically investigates the impact of bleeding on quality of life which would be suitable for use with AF patients. The study will instead utilize three previously validated general and disease-specific HRQoL measures EQ-5D, Perception of Anticoagulant Treatment Questionnaire (PACT-Q) and Atrial Fibrillation Effect on QualiTy-of-life (AFEQT).

6 STUDY CONDUCT

6.1 Ethics Committee Review and Informed Consent

6.1.1 Ethics Committee Review

The required approval from the <> Research Ethics Committees, and Swansea Bay University Health Board R&D approvals will be obtained before study site initiation. All approvals will be sought through Health and Care Research Wales using the Integrated Research Application System (IRAS).

The study research governance sponsor will be Swansea University ([contact]).

6.1.2 Informed Consent

In accordance with local regulations, subjects should provide written consent before enrollment into the study. Investigators must ensure that patients, are clearly and fully informed about the purpose of the study, potential risks, and the patient's rights and responsibilities when participating in this study.

6.2 Responsibilities within the Study

The Principal Investigator (PI) of this study is [name], Swansea Trials Unit (STU). Swansea University (SU). Swansea University will be the Sponsor of this study under the UK Policy Framework for Health and Social Care Research. BMS have agreed to fund the study and will provide oversight of the scientific quality and value for money of the protocol.

The study shall be conducted as described in this approved protocol. All revisions to the protocol must be discussed with, and authorised by, the study sponsor Swansea University and the funder BMS.

6.2.1 Sponsor Roles and Responsibilities

The Sponsor will assume overall responsibility for the study design, conduct, analysis and interpretation, as well as report writing and dissemination of results.

A representative from the funder, will sit on the Trial Steering Committee and will ensure that the protocol is well designed, scientifically valid and provides value for money.

6.2.2 *Principal Investigator Roles and Responsibilities*

The PI is ultimately responsible for the conduct of the study as a whole, regardless of dissemination of study tasks. The PI will ensure that the study is conducted in accordance with the protocol and that tasks are delegated appropriately. The PI will oversee research staff and ensure wellbeing of study participants.

6.2.3 *Steering Committee*

Trial Steering Committee (TSC)

Members of the trial steering committee will include sponsor representatives, study PI, research nurses, PPI representatives, trial manager and governance staff. The TSC will provide supervision of the study, make timely decisions on study set-up and conduct and monitor key milestones set out for the study. Meetings will occur monthly upon study set up (months 1-3) and quarterly (or as needed) for the remainder of the study.

Patient and Public Involvement

Two patient and public involvement (PPI) representatives will be selected at study outset and invited to contribute to study design, selection of appropriate data collection methods/tools and to attend study steering meetings. PPI's will be selected based on appropriate relatedness to the condition, such as those currently living with AF and prescribed anticoagulants and/or those involved with AF support groups (e.g. Heart Rhythm Alliance).

6.3 *Confidentiality of Study Data*

The confidentiality of records that could identify patients within the database must be protected, respecting the privacy and confidentiality rules in accordance with the applicable regulatory requirement(s).

For the purposes of protecting a patient's identity, a unique study code will be assigned to each patient, such as a series of numbers and/or letters. The data that is recorded with the patient's assigned code is called "key-coded data". Key-coded study data will be managed by the sponsor and/or its delegates in a study-specific electronic database (the "study database"). Only the site staff will have access to the link

between patient's assigned code and the patient's identity. However, in case of an audit or inspection, subject to local laws and regulations, government officials, REC representatives and sponsor representatives may access this information at the study site. If the study requires on-site monitoring, subject to local laws and regulations, sponsor representatives will also access the primary data source at the study site (see section 6.4). Data that could directly identify the patient will not be collected in the "study database".

Data will be processed in accordance with the Data Protection Act (2018) and GDPR (2016). All information collected about participants will be kept strictly confidential.

6.4 Quality Control

Representatives of the study sponsor must be allowed to visit all study site locations to assess the data quality and study integrity. On site, they will review study files and, patient medical notes to compare them with source documents, discuss the conduct of the study with the investigator, and verify that the facilities remain acceptable.

6.5 Database Retention and Archiving of Study Documents

The investigator must retain all study records and source documents for 10 years. The investigator must contact Swansea University prior to destroying any records associated with the study. Location of database and supporting documentation will be outlined in the final observational study report. Data will be securely stored and only accessible by the research team and will be carefully maintained and available for a minimum of ten years after completion of the study.

6.6 Registration of Study on Public Website

This study will be registered on ClinicalTrials.gov. The study will also be adopted into the NIHR CRN portfolio.

7 ADVERSE EVENT REPORTING

This study is not designed to capture safety events on any medicinal product and therefore, adverse event collection and reporting is not required.

Consideration has been taken for the possibility that patients may become distressed or emotional during completion of patient questionnaires by the recollection of previous experiences associated with bleeds. Patients may also experience low mood or anxiety associated with their condition. Both primary and

secondary care researchers have clinical experience of working with patients with low mood, anxiety and distress. If a participant reports, or shows signs of low mood, distress or anxiety they will be encouraged to discuss this with their primary or secondary care researcher and will be signposted to local relevant services or to contact their GP

Patients will have the right to withdraw at any point of the study. This will not affect their NHS care and this will be explained in the patient information sheet and any discussions. Should a distressed patient wish to continue participation, they will be given adequate time to complete questionnaires, taking into account any breaks the patient may wish to take. The patient information sheet contains contact details for researchers involved in the study and for the patient advice and liaison service (PALS) with information on how to contact both.

8 LIST OF ABBREVIATIONS

Term	Definition
A&E	Accident and Emergency
AF	Atrial Fibrillation
BARC	Bleeding Academic Research Consortium
BMS	Bristol-Myers Squibb
CRF	Case Report Form
EC	European Commission
ED	Emergency Department
ESC	European Society of Cardiology
GCP	Good Clinical Practice
GDPR	General Data Protection Regulations
GP	General Practice/General Practitioner
HRA	Health Research Authority
HRQoL	Health Related Quality of Life
ICMJE	International Committee of Medical Journal Editors
IRAS	Integrated Research Application System
IRB	Institutional Review Board
ISTH	International Society on Thrombosis and Haemostasis

JCRF	Joint Clinical Research Facility
NYHA	New York Heart Association
OAT	Oral Anticoagulant Therapy
PI	Principal Investigator
PROM	Patient Reported Outcome Measure
QoL	Quality of Life
REDCap	Research Electronic Data Capture
STU	Swansea Trials Unit
TIA	Transient Ischaemic Attack
TSC	Trial Steering Committee
VAS	Visual Analogue Scale

